4.2 Exclusion Criteria

- 1. Failure to meet any of the criteria set forth in the Inclusion criteria section
- 2. Previous systemic exposure to anti-CTLA-4 antibody or anti-PD1 antibody
- 3. Previous liver-directed treatments including chemoembolization, radiosphere, hepatic arterial perfusion, or drug-eluting beads; liver resection and focal ablation are permitted.
- 4. Presence of symptomatic liver failure including ascites and hepatic encephalopathy.
- 5. Presence of untreated brain metastases. If patients have had previous treatment for the brain metastasis, an MRI or CT scan of the brain must confirm the stabilization of the brain metastasis for more than 2 months.
- 6. Presence of uncontrolled hypertension or congestive heart failure, or acute myocardial infarction within 6 months of entry.
- 7. Presence of any other medical complication that implies survival of less than six months
- 8. Uncontrolled severe bleeding tendency or active GI bleeding.
- 9. Significant allergic reaction to contrast dye or GM-CSF.
- 10. Immunosuppressive treatments within 4 weeks prior to embolization, unless prednisone ≤ 5mg or equivalent
- 11. Pregnancy or breast-feeding women.
- 12. Patients with active hepatitis with SGOT and SGPT equal or greater than 5 times normal
- 13. Biliary obstruction, biliary stent or prior biliary surgery except cholecystectomy
- 14. Positive for known HIV Infection

- 15. Uncontrolled Chronic Obstructive Pulmonary Disease or previous known pulmonary fibrosis
- 16. Active infection.
- 17. Auto-immune disease including inflammatory bowel disease, lupus, rheumatoid arthritis, but not including hypothyroidism or psoriasis if condition has been stable for 2 months or greater.

4.2.1 Guidance for Women of Child Bearing Potential

Women must not be pregnant or breast-feeding. All females of childbearing potential must have a blood test or urine study within 2 weeks prior to start of treatment to rule out pregnancy. A female of childbearing potential is any woman, regardless of sexual orientation or whether they have undergone tubal ligation, who meets the following criteria: 1) has not undergone a hysterectomy or bilateral oophorectomy; or 2) has not been naturally postmenopausal for at least 24 consecutive months (i.e., has had menses at any time in the preceding 24 consecutive months).

Women of child-bearing potential must use at least two other accepted and effective methods of contraception and/or to abstain from sexual intercourse for at least 23 weeks after the last dose of nivolumab and/or ipilimumab and sexually active males must use at least two other accepted and effective methods of contraception and/or to abstain from sexual intercourse for at least 31 weeks after the last dose of nivolumab and/or ipilimumab. Should a woman become pregnant or suspect she is pregnant while she is participating in this study, she should inform her treating physician immediately.

4.3 Early Withdrawal of Subjects

4.3.1 When to Withdraw Subjects

An individual subject will not receive any further investigational product if any of the following occur in the subject in question:

- 1. Withdraw of consent or lost to follow up.
- 2. Subject is determined to have met one or more of the exclusion criteria and continuing therapy may be a safety risk
- 3. Pregnancy or intent to become pregnant
- 4. Any adverse event that meets criteria for discontinuation
- 5. Subject non-compliance that in the opinion of the investigator or sponsor warrants withdrawal
- 6. Initiation of alternative anti-cancer therapy
- 7. Confirmation of progression of disease

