5.0 STUDY DRUG/THERAPY

- GM-CSF, Ethiodol, and Gelatin Sponge as part of IEMBO will be given as standard of care in this study.
- Ipilimumab and Nivolumab will be given as investigational in this study.

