If patients have stabilization of hepatic metastasis but progression of extra-hepatic metastasis after 4 treatments, two additional IEMBO treatments, 4 weeks apart, will be allowed as long as hepatic metastasis is stable. This would prevent the early removal of patients with pseudo-progression of extra-hepatic metastasis. If follow-up imaging studies show further progression of extra-hepatic metastasis after 2 additional IEMBO + NIVO treatments, patients will be removed from the study. In that case, patients will be followed every 3 months to document their medical condition until their death. Follow-up over the telephone will be performed for patients unable to return for examination.

After the completion of first four treatment cycles, if disease stabilization is determined (at 12 weeks), continuation of treatment on maintenance phase may be offered as a combination of IEMBO +NIVO or, in the event of NIVO-related toxicity, IEMBO alone.

6.1.5 Additional outpatient visits prior to infusion of IPI+NIVO or NIVO alone. Patients will be seen in the outpatient setting prior to each infusion of IPI+NIVO or NIVO alone during maintenance.

During maintenance phase, after the completion of every two treatments patients will be seen by both medical oncology and interventional radiology for evaluation. A complete physical examination will be done by a study physician.

CT scan of the chest (with contrast), CT of abdomen and pelvis (with and without contrast) and MRI of the abdomen (with and without contrast) will be obtained prior to the subsequent follow-up office visits after every two treatments (NIVO + IEMBO).

The decision to continue treatment will be based on the results of the imaging and laboratory tests and the physical status of the patients. Unless patients become ineligible based on the inclusion/exclusion criteria, or unless patients develop rapid progression, or unless patients experience an unacceptable serious adverse event, the combination treatment will be continued.

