6.1.6 Completion of the study

Patients will receive study treatment for a maximum of two years or until disease progression. The study will be completed if progression of liver metastases is confirmed by the follow-up imaging studies. Patients will also be removed if they develop progression of extra-hepatic metastases for two consecutive imaging studies unless palliative radiation or surgical resection of progressive disease is feasible. Patients will be removed if they develop an unacceptable serious adverse event. If they fail to fulfill the eligibility criteria for the combination treatment, the patient will also be removed from the study.

At the time of study completion, the following studies and procedures will be performed:

- 1. Medical history to include determination of tumor-related symptoms
- 2. Physical examination to include ECOG performance status, weight, and vital signs
- 3. CT of the chest (with contrast), CT of abdomen and pelvis (with and without contrast), and MRI of the abdomen (with and without contrast)...if they are not ordered within 4 weeks of completion of the study
- 4. Blood draw for tests to include the following:
 Routine: complete blood count (CBC) with differential white blood count, serum laboratory studies including total bilirubin, SGOT, SGPT, LDH, alkaline phosphatase, albumin, TSH, creatinine, BUN, glucose, calcium, and phosphorus; Research: biomarker testing (60 ml) and immunological testing (10 ml).

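### For a patient with a stable liver and extra-hepatic progression on two consecutive scans that can be irradiated or resected, sections 4.3.1, 6.1.4, 6.1.5 and 6.1.6 give opposing instructions on stopping

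*Combined protocol and SAP*

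**What the plan says.** Section 4.3.1 opens its list of withdrawal criteria with "An individual subject will not receive any further investigational product if any of the following occur in the subject in question". Item 7 of that list is "Confirmation of progression of disease". Section 5.0 identifies the product concerned: "Ipilimumab and Nivolumab will be given as investigational in this study". The embolization components have a different status: "GM-CSF, Ethiodol, and Gelatin Sponge as part of IEMBO will be given as standard of care in this study".

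Section 6.1.4 has two relevant paragraphs.
- One removes a patient for extra-hepatic progression only where it calls for a switch of systemic treatment. It leaves palliative radiation or surgery to the investigator.
- The other covers a stable liver with extra-hepatic progression after four treatments. It allows two more treatments, and then, if follow-up scans "show further progression of extra-hepatic metastasis after 2 additional IEMBO + NIVO treatments, patients will be removed from the study". It makes no allowance for local treatment.

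Section 6.1.5 lets a patient without clinical deterioration continue past a first RECIST progression until the next scheduled scan. If that scan shows further growth, the progression is taken as real and the patient leaves the study. Local treatment is again not mentioned.

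Section 6.1.6 says: "Patients will also be removed if they develop progression of extra-hepatic metastases for two consecutive imaging studies", but adds "unless palliative radiation or surgical resection of progressive disease is feasible". The same section begins by limiting treatment to two years or to disease progression, without qualification. Section 5.6 permits palliative radiation while on treatment.

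**The concern.** A patient with a stable liver, extra-hepatic growth on two scans in a row and a lesion that can be irradiated or resected meets the conditions of all these rules. Some end treatment or study participation, and others do not. No section refers to another on this point, gives an order of precedence, or says whether a patient kept under 6.1.6 receives nivolumab with IEMBO or IEMBO alone.

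Two investigators following the protocol in good faith could therefore treat the same patient differently. Nivolumab exposure and the toxicity rates would then depend partly on which section was consulted. Hepatic PFS, a secondary endpoint in 3.3, could be affected as well. Liver measurements follow every second IEMBO treatment (6.1.5, 9.4), while follow-up after leaving the study is three-monthly and may be by telephone (6.1.4, 6.1.7).

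**Working it through.** No figure in the plan is at issue, so the check sets the rules side by side for one patient: liver stable, extra-hepatic disease growing on two consecutive scans, lesion suitable for radiation or resection.

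| Section | Trigger | Local-treatment exception | Result for this patient |
|---|---|---|---|
| 4.3.1 no. 7 | Confirmed progression, any site | None | No further ipilimumab or nivolumab |
| 6.1.4, paragraph on removal at the visit after 4 cycles | Extra-hepatic progression needing a switch of systemic treatment | Radiation or surgery allowed | Stays unless a switch is needed |
| 6.1.4, paragraph on two extra treatments | Further extra-hepatic progression after them | None | Removed from study |
| 6.1.5 | Further growth on the next scan | None | Removed from study |
| 6.1.6 | Extra-hepatic progression on two scans in a row | Radiation or resection feasible | Not removed |

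**Which drug is affected.** Scans fall between cycles 2 and 3 and then after cycle 4 (3.1, 9.1). The earliest possible second progressing scan is therefore the one after cycle 4. By then the four ipilimumab doses would normally have been given, so in practice the conflict mainly concerns nivolumab.

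**Does 6.1.6 imply continued nivolumab?** It says only that the patient is not removed. Two other statements point towards continued nivolumab. Section 6.1.5 continues the combination unless there is ineligibility, rapid progression or an unacceptable serious adverse event. Section 6.1.4 describes the two treatments given after extra-hepatic progression as IEMBO plus nivolumab. IEMBO alone is described for toxicity (3.1, 6.1.4, 6.3.3), not for progression. Continued nivolumab is the natural reading, but it is inferred and not stated.

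**Length of the difference.** Maintenance treatments are 4 weeks apart (5.4) and scans follow every two IEMBO treatments, so one further scan interval is 2 × 4 = 8 weeks.

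**Imaging.** By 5.0, the operative sentence of 4.3.1 covers ipilimumab and nivolumab only. It does not itself stop IEMBO or the scans tied to it. Loss of scheduled liver imaging follows from removal from the study under 6.1.4 or 6.1.5.

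**Primary endpoint.** It is hepatic response after four treatments (7.2.2), and the liver scan made then coincides with the earliest second progressing scan. As background, the two-stage design was recomputed with exact binomial sums:
- Early stop: P(X₁ ≤ 8) for n = 13 at 60% is 0.647.
- Rejection: the sum over x₁ = 9 to 13 of P(X₁ = x₁) × P(X₂ ≥ 26 − x₁), with 22 second-stage patients, is 0.0499 at 60% and 0.808 at 80%.

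These agree with the stated 0.65, 0.05 and 80% after rounding. The conflict does not alter them.

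**The case against.** The strongest reply is that 4.3.1 no. 7 is one line in a general list, that it does not define confirmation, and that the detailed sections should govern. Section 6.1.6 speaks of confirming progression in the liver and handles extra-hepatic disease separately, so item 7 could be read through it. Alternatively, a patient kept under 6.1.6 might receive IEMBO alone, which is not investigational, so that 4.3.1 would be respected.

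Either reading could reconcile 4.3.1 with 6.1.6. Neither resolves the rest. The second 6.1.4 paragraph, 6.1.5 and 6.1.6 are all detailed rules about removal from the study, and they still disagree.

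Parts of the reply do stand:
- A reader might infer that 6.1.4 as a whole allows no exception. It does not say that: its other paragraph comes close to the 6.1.6 exception. Section 6.1.4 is divided within itself.
- A reader might infer that 4.3.1 ends liver imaging. As shown above, it does not do so on its own terms.
- Section 9.6 records the date and sites of progression and measures hepatic and extra-hepatic intervals both separately and together. Continued treatment therefore need not erase a systemic progression event.

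**Conclusion.** The inconsistency is real and lies in the current text. It affects nivolumab exposure, the toxicity rates and, where a patient is removed, continued liver imaging for hepatic PFS. It does not directly affect the primary endpoint. The conclusion assumes that progression on two consecutive scans counts as confirmed, which 4.3.1 leaves undefined but 6.1.5 supports by its use of the next scan.

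The number of patients affected is unknown. Section 1.1 says the liver remains the only metastatic site in more than half of patients, and a reader might infer that up to 17 of 35 could be affected. The documents do not support that. The statement concerns having extra-hepatic disease at all. The conflict requires progression on two scans during treatment, a stable liver and a lesion suitable for local treatment, and no rate is given for that combination.

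A reader might also infer that both checkpoint drugs are equally at issue. On the planned scan schedule, ipilimumab would normally be complete.

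**What to change.** Reconcile 4.3.1 no. 7, both paragraphs of 6.1.4, 6.1.5 and 6.1.6 into one rule for extra-hepatic progression with a stable liver, and refer to it from each section. Which rule stands is for the sponsor to decide. The text should say what counts as confirmation, whether suitability for local treatment is an exception, and which of ipilimumab, nivolumab and IEMBO the rule covers.

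Add a REDCap field recording when a patient continues under any exception. In the analysis plan, count the first extra-hepatic progression as the systemic PFS event whether or not treatment continues, and align this with 9.6, which measures PFS to confirmation.

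Do not add a hepatic PFS analysis that leaves these patients out. They are identified by a post-baseline event that requires a stable liver, so excluding them would bias hepatic PFS, most plausibly downward.

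The cost is wording in four protocol sections, a sentence in the analysis plan and one data field. No extra patients or procedures are needed.

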4.3.2 Data Collection and Follow-up for Withdrawn Subjects

Subjects who are withdrawn from the study and permanently discontinued from receiving on study treatment will be followed for safety, including the collection of any protocol-specified blood specimens, unless consent if withdrawn or the subject is lost to follow up or enrolled in another clinical trial. All subjects will be followed for survival. Any subjects who are unable to return to the site for visits will be offered to follow up by phone every three months for at least one year.

4.3.3 Replacement of Subjects

Should a subject be withdrawn from the study prior to the assessment at the fourth cycle for any other reason besides clinical deterioration or toxicity they will be replaced as they will not be evaluable.

5.0 STUDY DRUG/THERAPY

- GM-CSF, Ethiodol, and Gelatin Sponge as part of IEMBO will be given as standard of care in this study.
- Ipilimumab and Nivolumab will be given as investigational in this study.

5.1 Drug Descriptions/Formulation/Procurement

Receipt of Study Drug Supplies [ipilimumab and nivolumab]

Upon receipt of the of the study treatment supplies, an inventory must be performed and a drug receipt log filled out and signed by the person accepting the shipment. It is important that the designated study staff counts and verifies that the shipment contains all the items noted in the shipment inventory. Any damaged or unusable study drug in a given shipment (active drug or comparator) will be documented in the study files. The investigator must notify study sponsor of any damaged or unusable study treatments that were supplied to the investigator's site.

5.1.1 GM-CSF (yeast-derived recombinant human GM-CSF)

- Other Names; Leukine®, Sargramostim
- Classification: Hematopoietic growth factor
- Mode of Action: Stimulates proliferation and differentiation of hematopoietic progenitor cells. Increases the cytotoxicity of monocytes toward certain neoplastic cell lines and activates polymorphonuclear neutrophils to inhibit the growth of tumor cells (41).
- Storage and stability: Leukine Liquid (500 mcg/ml) will be refrigerated at 2-8 °C until use. The Leukine Liquid may be stored for up to 20 days at 2-8 °C once the vial has been entered.
- Preparation: Three vials of Leukine Liquid (500 mcg) will be used to make a 2,000 mcg GM-CSF solution in 4 ml.
- Side Effects: In uncontrolled Phase I/II studies with Leukine® in 215 patients, the
 most frequent adverse events were fever, asthenia, headache, bone pain, chills and
 myalgia (>10%). These systemic events were generally mild or moderate and were
 usually prevented or reversed by the administration of analgesics and antipyretics
 such as acetaminophen. In these uncontrolled trials, other infrequent events
 reported were dyspnea, peripheral edema, and rash.
 - Reports of events occurring with marketed Leukine® include arrhythmia, fainting, eosinophilia, dizziness, hypotension, injection site reactions, pain (including abdominal, back, chest, and joint pain), tachycardia, thrombosis, and transient liver function abnormalities (<1% occurrence post-marketing).
 - In patients with preexisting edema, capillary leak syndrome, pleural and/or pericardial effusion, administration of Leukine® may aggravate fluid retention. Body weight and hydration status should be carefully monitored during Leukine® administration. Occurred 1% patients.

- In patients with preexisting liver or renal insufficiency, increased creatinine or bilirubin and hepatic enzymes would be observed. Transient increase of WBC counts may develop after the local infusion of GM-CSF into hepatic artery.
- Rarely, patients have developed acute allergic reactions or hemiplegia (<1% occurence).

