Diagnosis and Main Inclusion Criteria	 Inclusion criteria: Histologically confirmed metastatic uveal melanoma in the liver. Patients must have at least one measurable liver metastasis that is ≥ 10 mm in longest diameter by CT scan or MRI. The total volume of the tumors must be less than 50% of the liver volume. Willingness and ability to give informed consent. ECOG performance status of 0, or 1 Adequate renal and bone marrow functions: serum creatinine ≤ 2.0 mg/dl, granulocyte count ≥ 1000/mm3, and platelet count ≥ 100,000/mm3. Adequate liver function: bilirubin ≤ 2.0 mg/ml, albumin ≥ 3.0 g/dl, PT/PTT less than 1.5 times of upper normal limit (UNL), and AST and ALT less than 3.0 and alkaline phosphatase less than 1.5 times of UNL. Age ≥ 18 years of age. 			
Study Therapy, Dose, Route, Regimen	 Recombinant human GM-CSF (Sargramostim, Leukine®, Sanofi US). GM-CSF 1,500 mcg) will be mixed with ethiodized oil (Ethiodol®). The GM-CSF/ethiodized oil mixture will be injected selectively into one of the hepatic lobes. This will be followed by infusion of gelatin sponge particles to achieve the stasis of blood flow (immunoembolization). This will repeat every 3 weeks x 4 then every 4 weeks Ipilimumab (Yervoy) at 1mg/kg every 3 weeks x 4 doses. Nivolumab (Opdivo) at 3mg/kg every 3 weeks x 4, then flat dose 480mg every 4 weeks. 			
Duration of administration and follow-up	Patients will receive combination treatment of immunoembolization, ipilimumab, and nivolumab every 3 weeks for 12 weeks and in patients with CR, PR, and SD at 12 weeks, maintenance therapy with combination immunoembolization and nivolumab every 4 weeks will be offered until disease progression or unacceptable toxicity, for a maximum of 2 years. Follow-up contact will take place every 3 months for minimum of one year or until death to determine clinical status.			

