5.2 Dose Rationale

Patients will receive immunoembolization using GM-CSF at dose of 1500mcg every 3 weeks for the first four treatments then offered every 4 weeks maintenance. In the phase 1 dose escalation study, there was no dose-limiting toxicity up to 2,000mcg of GM-CSF dose; however, there was possible negative correlation between very high serum GM-CSF levels and PFS in patients with small liver metastasis. Therefore, our current standard care treatment uses 1,500 mcg of GM-CSF to avoid potential detrimental effects of high-dose GM-CSF.

The dosing of IPI+NIVO noted to be IPI 1mg/kg and 3mg/kg for the first four doses has been studied in a number of cancer types. It has been shown to be safe, and with less toxicity as evidenced in [NCT01454102].

Regarding the dosing of nivolumab, following the combination IPI+NIVO dosing for the first four doses the every 4-week schedule (Q4W) of NIVO will be more convenient for subjects. Based on pharmacokinetic modeling, the 480 mg Q4W (after steady state is reached with 3 mg/kg or 240 mg every 2 weeks) will provide steady-state average concentrations similar to 3 mg/kg or 240 mg Q2W, which has been shown to provide longer survival in NSCLC patients. However, 480 mg Q4W is expected to result in higher (approximately 20%) steady-state maximum concentration (peaks), and lower (approximately 10%) steady-state trough concentrations compared to steady state of 3 mg/kg Q2W. Nivolumab was adequately tolerated up to 10 mg/kg, the highest dose level tested, and no maximum tolerated dose was identified. In addition, the exposure-response relationship for safety is flat. Thus, a slight increase in the steady-state maximum concentration is not expected to increase the safety risk of nivolumab. However, a marginal decrease in steady-state trough concentration is not expected to reduce the efficacy as high trough concentrations and > 90% intra-tumoral receptor occupancy are still maintained at 480 mg Q4W dose. Nivolumab 480 mg Q4W is expected to have similar efficacy and safety profile to 3 mg/kg Q2W.

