5.3.3 Embolization

For the patients who receive immunoembolization with GM-CSF, 3.5ml of Leukine® Liquid (1,500 mcg of GM-CSF) will be used. This solution will be emulsified in ethiodized oil (Ethiodol®) by repeated transfer of the two liquids between syringes connected via a stopcock. The amount of ethiodized oil administered is calculated based on tumor volume (1 ml per cm of summed tumor diameters). The actual amount of ethiodized oil will be decided based on the angiographic findings, including the degree of tumor vascularity and flow within the target hepatic artery. However, the maximum dose of ethiodized oil will not exceed 20 ml. The GM-CSF/ethiodized oil mixture will be done in the angiography suite immediately prior to the intraarterial delivery. When an emulsion has formed, the GM-CSF/ethiodized oil mixture will be slowly injected into the hepatic artery. Endpoints for the infusion of ethiodized oil will be delivery of the planned volume or the appearance of larger order portal vein branches. The perfusion pattern to the targeted tumors will be monitored during the injection of the ethiodized oil. Following this injection, gelatin sponge particles (1-2 mm size) will be infused into the hepatic artery until stasis of antegrade flow is obtained.

The immunoembolization procedure will be repeated every 3 weeks for the first 4 cycles and then if patient has shown evidence of tumor response, IEMBO may continue on maintenance every 4 weeks until disease progression or limiting toxicities. If the tumor is confined to a single lobe of the liver, embolization will be repeated to that lobe but interval between treatments may be extended up to every 6 weeks at the discretion of the treating physician. If the liver metastases are located in the both lobes of the liver, each hepatic lobe will be treated alternately. Variant arterial anatomy may require departure from this principle. Examples include a left lobe with dual supply from the left gastric artery and proper hepatic artery. The latter may be treated along with the right lobe.

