5.4 Treatment Regimen Combination

Patients will be seen in the outpatient office on Day #1 of every cycle and receive administration of ipilimumab and nivolumab or once in maintenance phase nivolumab alone. On Day #2 they will undergo IEMBO consisting of intra hepatic artery administration of GM-CSF (1500mcg) mixed with ethiodized oil emulsion, followed by embolization of the hepatic artery with gelatin sponge particles under the care of interventional radiology. Patients will undergo this combination intervention every 3 weeks for 12 weeks unless significant disease progression, limiting toxicity, or withdrawal of consent. Interim imaging after 2 cycles will be peformed to ensure there has not been rapid progression. After four combination treatments if noted to have CR, PR, or SD patients will be offered maintenance therapy with combination intervention every 4 weeks until disease progression, limiting toxicity, or withdrawal of consent. When undergoing every 4 week maintenance patients will receive NIVO on Day #1 and IEMBO on Day #2 of each 28 day cycle.

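### The GM-CSF preparation figures in sections 5.1.1 and 5.3.3 do not add up: three 500 mcg vials hold 1,500 mcg, not 2,000 mcg, and 3.5 ml at 500 mcg/ml holds 1,750 mcg, not 1,500 mcg

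*Combined protocol and SAP*

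**What the plan says.** The intended dose is consistent. The Study Summary, section 5.2, section 5.3.3 and section 5.4 all give 1,500 mcg; section 5.4, for example, has "administration of GM-CSF (1500mcg) mixed with ethiodized oil emulsion". Section 5.2 explains the choice. The phase 1 study went up to 2,000 mcg, and the centre uses 1,500 mcg because very high serum levels were possibly associated with shorter PFS in patients with small liver metastases.

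The preparation figures are in two places:

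- **Section 5.1.1** gives the product strength ("Leukine Liquid (500 mcg/ml) will be refrigerated") and then the preparation: "Three vials of Leukine Liquid (500 mcg) will be used to make a 2,000 mcg GM-CSF solution in 4 ml".
- **Section 5.3.3** gives the volume for the procedure: "3.5ml of Leukine® Liquid (1,500 mcg of GM-CSF) will be used".

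Neither section names a diluent. The revision history (section 15.4) lists no change to section 5.1.1. For section 5.3.3 it lists only a change to the interval between embolizations. Both sentences are therefore current text.

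**The concern.** These are operative instructions for a drug given at every embolization: four in the initial phase, then every 4 weeks for up to two years in all. A vial count, a strength, a volume and a mass must agree with one another, and here they do not. The only preparation line for GM-CSF ends at 2,000 mcg, the level that section 5.2 moved away from. The volume in section 5.3.3 does not give the mass written beside it.

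At stake is whether the dose in the syringe is the intended one. The written figures allow different doses depending on which of them the preparer follows. Immunoembolization is part of the regimen under test, so its dose should be stated unambiguously. The error rates and sample size do not depend on this point.

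**Working it through.** **Inputs**

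- Product strength: 500 mcg/ml (5.1.1)
- Vials and content: three vials of 500 mcg (5.1.1)
- Stated yield: 2,000 mcg in 4 ml (5.1.1)
- Stated volume and mass at embolization: 3.5 ml, 1,500 mcg (5.3.3)
- Intended dose: 1,500 mcg (Study Summary, 5.2, 5.3.3, 5.4)
- Assumption: a 500 mcg vial at 500 mcg/ml contains 1.0 ml, as those two figures imply. Overfill is not given.

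**Section 5.1.1: mass = vials × content per vial**

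- 3 × 500 mcg = 1,500 mcg. The stated 2,000 mcg is not reproduced.
- Excess: 2,000 − 1,500 = 500 mcg; 500 / 1,500 = 33.3%.
- For three vials to yield 2,000 mcg, each would need 2,000 / 3 = 666.7 mcg.
- 2,000 mcg / 4 ml = 500 mcg/ml, the strength of the undiluted liquid, and 2,000 / 500 = 4 vials. So the yield and the 4 ml fit each other and describe four undiluted vials. The vial count of three fits the 1,500 mcg dose.

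**Section 5.3.3: mass = volume × strength**

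- 3.5 ml × 500 mcg/ml = 1,750 mcg. The stated 1,500 mcg is not reproduced.
- Excess: 1,750 − 1,500 = 250 mcg; 250 / 1,500 = 16.7%.
- Volume that holds the intended dose: 1,500 / 500 = 3.0 ml, so 3.5 ml is 0.5 ml too much.
- Vials needed for 3.5 ml undiluted: 3.5 / 1.0 = 3.5, so a fourth must be opened. The protocol makes that feasible, since after a vial is entered "The Leukine Liquid may be stored for up to 20 days" at 2-8 °C.

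**Can any one reading satisfy both sections?**

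| Reading | Amount given | Difference from 1,500 mcg |
|---|---|---|
| Three whole vials, all given | 1,500 mcg | 0 |
| 3.5 ml drawn undiluted | 1,750 mcg | +250 mcg (+16.7%) |
| Three vials made up to 4 ml (375 mcg/ml), 3.5 ml drawn | 3.5 × 375 = 1,312.5 mcg | −187.5 mcg (−12.5%) |
| Three vials made up to 3.5 ml (1,500 / 3.5 = 428.6 mcg/ml), all given | 1,500 mcg | 0 |
| 4 ml at 500 mcg/ml, all given | 2,000 mcg | +500 mcg (+33.3%) |

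The fourth row would rescue section 5.3.3. It contradicts the 4 ml in section 5.1.1, though, and needs a dilution that neither section describes. No row satisfies both sections.

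**The case against.** The best defence concedes section 5.1.1 and contests section 5.3.3 and the weight of the point.

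**Dilution.** Section 5.3.3 does not say that the 3.5 ml is undiluted, and section 5.1.1 speaks of making up a solution. Three vials brought to 3.5 ml would hold exactly 1,500 mcg, so the fault may be an unstated diluent rather than a wrong volume. This cannot be excluded, but the text does not support it. Section 5.3.3 calls the liquid by the product name to which section 5.1.1 attaches 500 mcg/ml, no diluent appears, and section 5.1.1 gives 4 ml. The possibility is a reason to ask pharmacy before correcting the text. It does not make the text right.

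**Direction.** The 250 mcg excess arises only if 3.5 ml is drawn undiluted, and another reading gives 1,312.5 mcg, below the intended dose. That stands: the direction of any misdose is not established. It also confirms that the written volumes cannot safely be followed.

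**Consequence.** Section 5.2 says "there was no dose-limiting toxicity up to 2,000mcg of GM-CSF dose". Its caution is about a possible correlation with very high serum levels, and it gives no threshold between 1,500 and 2,000 mcg. So the fact that 1,750 mcg lies midway between them is only arithmetic. According to section 5.0, "GM-CSF, Ethiodol, and Gelatin Sponge as part of IEMBO will be given as standard of care in this study", and section 5.2 describes 1,500 mcg as existing practice at this single centre. Section 5.3.3 puts the mass beside the volume and allows the infusion to end early. All of this stands. It limits the likely harm and leaves the written instruction wrong.

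**Conclusion.** The concern holds. On the protocol's own figures, section 5.1.1 overstates the yield of three vials by 500 mcg (33.3%), and the 3.5 ml in section 5.3.3 holds 250 mcg (16.7%) more than the mass written beside it. The wrong items are the 2,000 mcg yield and the 4 ml and 3.5 ml volumes. The 1,500 mcg dose and the count of three vials are sound.

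The section 5.1.1 result needs only the stated content per vial. The section 5.3.3 result assumes that the 3.5 ml is the 500 mcg/ml product as named. The count of 3.5 vials also assumes 1.0 ml per vial without overfill.

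This should be fixed because it is a dose instruction, but the consequence is limited. Nothing in the documents shows that a patient was misdosed, and the Simon design, primary endpoint and analysis are unaffected.

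**What to change.** Ask pharmacy to confirm the vial strength and whether any diluent is used. Then:

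- **If undiluted:** state in both section 5.1.1 and section 5.3.3 that three 500 mcg vials are used, giving 3.0 ml at 500 mcg/ml, or 1,500 mcg. Delete the 2,000 mcg in 4 ml from section 5.1.1 and the 3.5 ml from section 5.3.3.
- **If diluted:** name the diluent, its volume and the final concentration in both sections, and state that the whole preparation is the 1,500 mcg dose.

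The cost is two corrected sentences and one pharmacy confirmation. No new data field is needed, and the design, sample size and analysis do not change.
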